11 SCHEDULE OF EVENTS

11.1 Schedule of Events Prospective Arm

	Screening	Day 0	Week 4	Week 12*	Week 24*	Day of Transplant	3M post treatment	6 M post treatment
			Month 1	Month 3	Month 6 if treated for 24 weeks	If transplant occurs post treatment with study drug	3 Months post treatment	6 Months or greater post treatment
History and Physical	X	X	X	X	X			X
Vital signs and Weight		X	X	X	X		X	X
Height	X							
Urinalysis		X						
Pregnancy Test: Urine		X ¹						
HBsAg	X							
Anti-HBc	X							
Virology Panel: (Historical only)								
Anti-HIV Ab	X							
Anti-HCV Ab	X							
HCV Genotype	X							
Plasma HCV RNA Levels		X	X	X	X		X	X
CD4+ T-cell count		X ²		X ²	X ²		X ²	X ²
HIV-1 RNA (bDNA or PCR)		X ²		X ²	X ²		X ²	X ²
Standard of care liver staging	X			X ³	X			
SERUM CHEMISTRY								
Alanine aminotransferase (ALT)		X	X	X	X		X	X
Albumin		X		X	X			X
Alkaline phosphatase		X	X	X	X		X	X
Aspartate aminotransferase (AST)		X	X	X	X		X	X
Bicarbonate (If on ARV regimen containing tenofovir)		X	X	X	X		X	X
Bilirubin, total, direct		X	X	X	X		X	X
Glucose (repeat during treatment, but only if abnormal at baseline)		X	X	X	X			
Phosphate (If on ARV regimen containing tenofovir)		X	X	X	X		X	X
Potassium (If on ARV regimen containing tenofovir)		X	X	X	X		X	X
Sodium		X	X	X	X		X	X
Serum Creatinine		X	X	X	X		X	X
HEMATOLOGY								
Hemoglobin		X		X	X			
Platelet Count		X		X	X			
White Blood Cell (WBC) Count		X		X	X			
Differential		X		X	X			
Neutrophils		X		X	X			
Lymphocytes		X		X	X			
INR		X		X	X			
RESEARCH								

Limited HCV Viral Kinetics		X	X	X	X			
Liver explant tissue (if achieved SVR)						X ⁴		
HLA	X ²							
Blood draw for immunologic studies		X	X	X	X		X	X
Paxgene DNA (6.5 ml)		X						
Paxgene RNA (2.5 ml)		X	X	X	X		X	
IL28B rs12979860 (run off Paxgene DNA sample)		X						
Blood for storage (8 cc SST serum, 6 cc EDTA)		X	X	X	X		X	X

*Subjects who are terminated early or who have early treatment discontinuation should have an end of treatment visit as soon as possible after therapy is stopped.

¹ Urine pregnancy test for females with childbearing potential must be negative on Day 0 prior to dosing with study agent

² documented historic results are acceptable. If not available, not required unless considered standard of care, or may be run on stored samples. For HIV-1 RNA and CD4+ T-cell counts, test results from primary care provider should be obtained per standard of care (every 3 months)

³only if treatment stops at week 12. Performed at screening and end of treatment

⁴ Liver explant tissue collected and snap frozen or placed in RNA- *later* at the time of transplant, but only if subject achieved SVR pre-transplant.

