3.2 Prospective Arm

The cohort of pre-transplant patients with cirrhosis due to hepatitis C will be treated with SOF/LDV until LT or for a maximum of 24 weeks. Patients with and without HCC within Milan criteria are eligible. Another cohort of liver transplant recipients with recurrent HCV infection post liver transplant will also be treated with SOF/LDV for a period of 12 weeks (no cirrhosis) or 24 weeks (cirrhosis). Patients with fibrosing cholestatic hepatitis are eligible and will be treated for 12 weeks.

Starting with Day 0, all subjects will receive SOF/LDV for 12 or up to 24 weeks. The total amount of time required to complete all the study visits is approximately 56 - 68 weeks from the screening period through the end of the follow-up visits:

- Up to 8 weeks Screening period
- 12 or 24 week treatment period
- 12 and 24 week post-treatment follow-up visits (SVR12 and SVR24)
- 36 weeks post-treatment to assess late viral relapse

Subjects identified to have mutations leading to SOF or LDV resistance following sequencing and phenotypic analysis will be requested to return at 12-week intervals for up to 36 weeks to determine the time required for the resistant virus to return to background levels.

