4.2.2 Safety Population

The primary analysis set for safety analyses will include subjects who received at least one dose of study drug.

On treatment data will be analyzed and defined as data collected from the first dose of study drug through the date of last dose of study drug plus 30 days.

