7.10 Early Termination and Early Treatment Discontinuation

Participants who elect to discontinue study drugs prior to treatment completion for medical or personal reasons will be given the option of being followed up at least every 12 weeks for safety and research labs until the end of the study. The participant should have an end of treatment visit scheduled as soon as possible after all therapy is discontinued. Participants with undetectable HCV RNA at the end of treatment should continue to follow the scheduled SVR visits following the date of their last dose of therapy.

For the prospective arm, participants who have detectable HCV RNA at the end of treatment or who relapse post-treatment will be asked to return for visits to determine the persistence of any HCV populations with treatment-emergent substitutions conferring resistance to sofosbuvir. Samples collected will be used to determine the durability of response or the dynamics of any changes in resistance conferring mutations. The reason for any early termination should be documented.

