8.6 Treatment of Participants

All participants will receive 12 or up to 24 weeks of SOF/LDV. SOF/LDV will be administered as a single pill at dose of 400 mg and 90 mg respectively orally once a day. It can be taken with or without food.

If a participant who starts treatment with study drug prior to transplant receives 4 weeks of treatment or less prior to transplant and has detectable HCV at time of transplant, they are eligible to receive full treatment post-transplant.

If a participant who starts treatment with study drug prior to transplant has received more than 4 weeks of treatment prior to transplant, they are NOT eligible to receive full treatment post-transplant, regardless of HCV RNA level at the time of liver transplantation. Therefore, study treatment is discontinued at the time of transplant.

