10.5.3 AE and SAE Recording/Documentation/Follow-up

Adverse events will be collected from the time treatment starts on Day 0 through the end of the study follow-up period. Serious Adverse Events will be collected during the treatment phase plus 30 days.

At each contact with the subject as outlined above, information regarding AEs will be elicited by appropriate questioning and examinations and will be immediately recorded on a source document. Source documents will include: progress notes, laboratory reports, consult notes, phone call summaries, survey tools and data collection tools. Source documents will be reviewed in a timely manner by the research team. The onset date, the end date, the severity of each reportable event, and the Investigator's judgment of the AEs relationship to SOF/LDV will also be recorded.

Adverse events will be followed at a minimum until resolution of the AE or a return to baseline laboratory value. SAEs that occur after the study follow-up period that are reported to and are assessed by the Investigator to be possibly, probably, or definitely related must be reported to the UCSF Project Manager and in the Redcap Database, as described above.

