10.5.4 Adverse Events and Serious Adverse Events Exempt from Reporting

Elective hospitalizations or hospital admissions for the purpose of conduct of protocol mandated procedures are not to be reported as an SAE unless hospitalization is prolonged due to complications.

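### Where SOF/LDV ends at transplant, the end-of-treatment visit and the 30-day on-treatment tail are post-operative, and the plan provides no pre-operative cut

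*Combined protocol and SAP*

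**What the plan says.** All references are to the combined protocol and SAP.

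- **Duration.** Section 3.2 says pre-transplant patients "will be treated with SOF/LDV until LT or for a maximum of 24 weeks". Transplant on drug is thus a foreseen route, not a deviation.
- **Drug at transplant.** Section 8.6 separates two cases. After more than 4 weeks of drug: "Therefore, study treatment is discontinued at the time of transplant". After 4 weeks or less with detectable HCV at transplant: "they are eligible to receive full treatment post-transplant".
- **End-of-treatment visit.** The 11.1 footnote says that subjects with "early treatment discontinuation should have an end of treatment visit as soon as possible after therapy is stopped". Section 7.10 agrees: "The participant should have an end of treatment visit scheduled as soon as possible after all therapy is discontinued".
- **On-treatment window.** Section 4.2.2 runs it from first dose "through the date of last dose of study drug plus 30 days". Section 10.5.3 uses the same length: "Serious Adverse Events will be collected during the treatment phase plus 30 days". Neither mentions transplant.
- **Day of Transplant column (11.1).** It applies only when transplant comes after study treatment, and its only entry is explant tissue in participants with SVR.
- **Exemption.** Section 10.5.4: "Elective hospitalizations or hospital admissions for the purpose of conduct of protocol mandated procedures are not to be reported as an SAE". A stay prolonged by complications is not exempt, and transplant is not named.

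**The concern.** Read together, these rules place the end-of-treatment assessment on the far side of the operation for anyone whose drug ends at transplant. Hemoglobin, platelets, INR, bilirubin, ALT and creatinine at that visit would be post-operative values in a patient with a new graft. HCV RNA for ETR would be measured after the infected liver has been removed. Section 4.3 summarises safety laboratory results by time point and as change from pre-dose, so these values would enter the SOF/LDV summaries unmarked.

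The 30-day tail does the same for events. A surgical complication of grade 3 or higher would count as an on-treatment event. In an arm of 10 to 20 participants, the summaries would then depend partly on how many candidates happened to receive an organ while on drug.

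**Working it through.** The plan gives no figure for this point, so there is none to reproduce. The check is the order of events, followed by an illustration of size.

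**1. Order of events, by route**

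| Route | Last dose | End-of-treatment visit | Last dose + 30 days |
|---|---|---|---|
| Treatment completed before transplant | Before surgery | Normally before surgery | May or may not reach surgery |
| More than 4 weeks of drug, then transplant | At transplant | After surgery | Operation and first post-operative month |
| 4 weeks or less, HCV detectable, full post-transplant course | After that course | After that course | Contains the operation and the whole later course |

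The second row is the point made here. The third row matters for the remedy. Section 8.6 gives no rule for 4 weeks or less with undetectable HCV.

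**2. Does another section repair the second row?** The Day of Transplant column does not cover it. Causality grading (10.4) applies to single events; laboratory values have no such grade, and 4.2.2 is not limited to related events. Section 4.4.2 defers only efficacy details to a statistical analysis plan.

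**3. Post-operative share of the window.** With T days on drug before a transplant that ends treatment, the share is 30/(T + 30):

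- T = 29: 30/59 = 51%
- T = 84: 30/114 = 26%
- T = 167: 30/197 = 15%

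**4. How many participants.** The documents give the arm size (10, up to 20; section 3.0) and an expected wait of at least 12 weeks (5.2, inclusion item 14). The rest is assumed: half the arm are candidates, all are treated towards 24 weeks, and the median further wait m after Week 12 is 12 to 36 weeks, with a constant hazard.

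P(transplant in Weeks 12 to 24) = 1 − 0.5^(12/m):

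- m = 12: 0.50
- m = 24: 0.29
- m = 36: 0.21

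With 5 candidates (n = 10) and the longest wait, 0.21 × 5 is about 1. With 10 candidates (n = 20) and the shortest wait, 0.50 × 10 = 5. If candidates complete treatment before transplant, the number is 0. The range is 0 to about 5.

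**5. Effect on a proportion.** One participant with an event who would otherwise have had none adds 1/20 = 5 points or 1/10 = 10 points. Now assume a 20% background of grade 3+ events and a probability p of such an event within 30 days of surgery. With k participants transplanted on drug, the on-treatment proportion is (k·p + (n − k)·0.20)/n:

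- n = 20, k = 0: 20%
- n = 20, k = 2, p = 0.7: (1.4 + 3.6)/20 = 25%
- n = 20, k = 5, p = 1.0: (5 + 3)/20 = 40%

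The 20% and the 0.7 to 1.0 are assumptions with no source in the documents.

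**The case against.** **The footnote may not apply.** It concerns early discontinuation, and 7.10 speaks of participants who choose to stop. Treatment up to transplant is the planned course in 3.2. This is a fair reading, but it does not help. Section 7.7 ties the end-of-treatment visit to Week 12 or 24, so for a stop at Week 18, say, the next such visit is Week 24, still after surgery. Neither reading yields a pre-operative end-of-treatment assessment.

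**Pre-operative values exist.** A reader might infer that there are no on-treatment data before surgery. That is wrong for transplants after Week 12: the Week 12 column carries chemistry, hematology, INR and HCV RNA, and 7.6 adds visits at Weeks 16 and 20 where applicable, with HCV RNA at each. What is missing is a rule that uses them as end-of-treatment values.

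**The plan tries to avoid the situation.** Section 5.2 expects transplant at least 12 weeks away so that treatment can be completed, and the design rationale in 1.1 gives candidates 12 to 24 weeks. This stands, and it is why the count can be zero.

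**The primary results look contaminated.** A reader might infer this too, but the documents do not support it. The primary safety endpoint (4.1.3) is an AE leading to permanent discontinuation, and drug has already stopped when post-operative events occur. SVR12 is counted from the end of therapy and does not use the end-of-treatment visit. Nor does 4.5 plan a safety comparison of candidates with recipients that could be invalidated.

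**An inclusive all-cause window is a defensible safety rule.** This also stands. Simply ending the window at surgery would take early post-operative deaths and SAEs out of the on-treatment table. Applied to everyone on drug at transplant, it would also remove the entire later course of a participant treated in full afterwards under 8.6.

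**Conclusion.** The point holds for prospective-arm candidates whose SOF/LDV ends at transplant after more than 4 weeks. For them the plan has no pre-operative end-of-treatment assessment and no separation of peri-operative data. The effect falls on end-of-treatment laboratory values, ETR, ALT normalisation, and the on-treatment AE, SAE and laboratory summaries.

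The sequence of events follows from the documents; the size does not. The range of 0 to about 5 of 20, and any rise from 20% to 25–40%, rest on the assumed candidate share, waiting time, treatment length and event rates. Only the 5 to 10 points per added event follow from the arm size alone. This is a cheap improvement to descriptive results, not a threat to the primary endpoints.

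**What to change.** Add to section 4.2.2 and the 11.1 footnote, as analysis rules:

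1. Where study drug ends at transplant, the end-of-treatment laboratory values and HCV RNA used for analysis are the last available sample before the operation. Report its date.
2. Keep the on-treatment table to last dose plus 30 days. Add a second on-treatment table cut at the start of the operation, with later events and laboratory values tabulated separately as peri-transplant.
3. Do not apply the cut to participants who receive full treatment after transplant under 8.6. Their post-transplant course stays on-treatment, with peri-operative events flagged.

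Every event is still collected, and dosing, duration and stopping rules are untouched. The cost is one extra table and some loss of timeliness, because the pre-operative value may come from an earlier scheduled visit. The schedule has no hematology or INR between Day 0 and Week 12, so for a transplant in that interval a post-baseline pre-operative value exists only if a local result is recorded; otherwise it should be shown as missing.

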11.2 Schedule of Events Retrospective Arm (Waiver of Consent)

	Screening	Day 0	Week 4	Week 12*	Week 24*	3M post treatment	6 M post treatment
			Month 1	Month 3	Month 6 if treated for 24 weeks	3 Months post treatment	6 Months or greater post treatment
Record Vital signs and Weight		X	X	X	X	X	X
Record Height	X						
Record Urinalysis		X					
Record Virology Panel: (Historical only)							
HBsAg	X						
Anti-HIV Ab	X						
Anti-HCV Ab	X						
HCV Genotype	X						
Record Plasma HCV RNA Levels		X	X	X	X	X	X
Record CD4+ T-cell count		X		X	X	X	X
Record HIV-1 RNA (bDNA or PCR)		X		X	X	X	X
Record Standard of care liver staging	X			X	X		
SERUM CHEMISTRY							
Record Alanine aminotransferase (ALT)		X	X	X	X	X	X
Record Albumin		X		X	X		X
Record Alkaline phosphatase		X	X	X	X	X	X
Record Aspartate aminotransferase (AST)		X	X	X	X	X	X
Record Bicarbonate (If on ARV regimen containing tenofovir)		X	X	X	X	X	X
Record Bilirubin, total, direct		X	X	X	X	X	X
Record Sodium		X	X	X	X	X	X
Record Serum Creatinine		X	X	X	X	X	X
HEMATOLOGY							
Record Hemoglobin		X		X	X		
Record Platelet Count		X		X	X		
Record White Blood Cell (WBC) Count		X		X	X		
Record Differential		X		X	X		
Record Neutrophils		X		X	X		
Record Lymphocytes		X		X	X		
Record INR		X		X	X		

11.3 Schedule of Events Retrospective Arm: One Prospective Visit

RESEARCH	Screening	Day 0
Informed Consent	X	
Return to site for liver staging by Fibroscan. Historical liver staging by Fibroscan or liver biopsy within the previous 12 months for standard of care is acceptable.		X

11.4

12 MECHANISTIC STUDIES: PROSPECTIVE ARM

Viral Kinetics

Samples from Days 0, week 4, and end of treatment (EOT) will be used to assess HCV viral load levels.

HCV Virologic Studies

Full length HCV genome pyro sequencing may be performed using the protocol as described and compared for variability of sequences [45].

rs12979860 (IL28B) Genetic Variant

IL28B genetic variants have been shown to predict HCV treatment induced clearance. The IL28B assay is a real-time PCR assay that utilizes 5-prime nuclease activity of a thermostable polymerase and unique primers and SNP-specific probes to determine the genotype. Test results will not be used as inclusion or exclusion criteria, or to randomize subjects into treatment groups.

Immune Responses to HCV and HIV

Both humoral and cellular immunity against HCV and HIV will be estimated before and during treatment to assess the effect of HCV treatment on host immune response against HCV. We may also perform multiplex PCR assays to detect ISGs before and during treatment.

HCV Genotypic and Phenotypic Resistance Monitoring

Serum samples for genotypic and phenotypic monitoring will be collected

Resistance monitoring will be completed in all subjects who received study drug and were virologic failures as defined.

Subjects who are determined by sequencing and phenotypic analysis to have had mutations leading to SOF resistance will be requested to return at 12 week intervals for up to 48 weeks after the last dose of study drug to determine the time for the resistant virus to return to background levels.

RNA Extraction from liver tissue

In addition, this protocol will also allow for exploration of the potential of an HCV viral reservoir after achieving the primary endpoint of SVR12. Subjects who receive treatment pre-transplant and achieve SVR, but who nonetheless progress to liver transplantation, will have a portion of the explanted liver snap frozen or placed in RNA- *later*. Subsequently, liver RNA will be extracted and an attempt will be made to amplify residual HCV RNA using a protocol adapted from (<http://www.ncbi.nlm.nih.gov/pubmed/22729600>) that is sensitive to 2 copies of HCV RNA/ug of total liver RNA. If RNA is able to be amplified, the relevant sequences of the HCV genome will be determined as above. The ability to obtain sufficient quantities of liver RNA for this analysis, given that the whole organ is explanted at transplant, is a unique opportunity to explore the possibility of residual HCV RNA after SVR in this cohort.

13 HAZARDS/DISCOMFORTS/RISKS: PROSPECTIVE ARM

13.1 Drugs

The combination of SOF/LDV is well tolerated with minimal adverse events. The safety profile of SOF includes approximately 1600 chronic HCV-infected subjects that have been administered over 12 weeks of SOF in combination with a DAA, PEG-IFN, and/or RBV. No clinical safety issues related to SOF have been identified to date. The safety profile of LDV includes over 1000 chronic HCV-infected subjects, of whom over 700 have been administered more than 12 weeks of LDV, which was given in combination with other DAAs, PEG-IFN, and/or RBV. No clinical safety issues related to LDV have been identified to date.

Furthermore, there is no expectation of significant overlapping or new, unexpected toxicities upon administration of SOF/LDV together as an FDC. To date, the SOF/LDV FDC ± RBV has been administered to over 500 HCV infected subjects in ongoing phase 2/3 trials, with over 200 subjects having received SOF/LDV FDC ± RBV for 12 weeks or more.

Risk of bradycardia: People taking beta blockers, or who have an underlying cardiac condition or advanced liver disease, may be at increased risk for bradycardia when taking Harvoni or Sovaldi with amiodarone.

Risk of Reduced Therapeutic Effect of Harvoni Due to P-gp Inducers: Rifampin and St. John's wort are not recommended for use with Harvoni as they may significantly decrease ledipasvir and sofosbuvir plasma concentrations.

Related Products Not Recommended: Harvoni is not recommended for use with other products containing sofosbuvir (Sovaldi).

Adverse Reactions

Most common ($\geq 10\%$, all grades) adverse reactions were fatigue and headache.

Resistance

An additional possible risk is the development of class resistance to NS5B inhibitors and NS5A inhibitors. Development of such resistance could affect future therapeutic options. However all efforts will be made to manage the development of class specific mutations that could lead to cross resistance to other NS5B and NS5A inhibitors.

13.2 Procedures

13.2.1 Phlebotomy

The primary risks of phlebotomy include occasional bleeding or bruising of the skin at the site of needle puncture, and the sensation of transient lightheadedness or rarely, fainting and infection. The amount of blood drawn will be within the limits allowed for adult subjects by the NIH CC.

14 HUMAN SUBJECT PROTECTIONS

Participants will be fully counseled prior to entry into the study as to the potential risks of the study. Participants who, in the opinion of the study team, do not fully comprehend these potential risks will not be offered participation in the study. Participants will be monitored closely during their participation in the study.

14.1 Gender, Ethnicity, and Race Considerations

Participants will not be excluded based on gender, ethnicity or race.

14.2 Children and Pregnant Women

This study will be limited to adults 18 aged years or older. Insufficient data are available to evaluate the safety and efficacy of SOF/LDV FDC in the pediatric population. No adequate human data are available to establish whether or not SOF/LDV FDC poses a risk to pregnancy outcomes. In animal reproduction studies, no evidence of adverse developmental outcomes was observed with SOF or LDV at exposures greater than those in humans at the recommended human dose. Any woman of child-bearing potential must have a negative urine pregnancy test on the first day of treatment (Visit 2/Day0) prior to receiving the first dose of FDC.

